## 11.6 Data Analysis Plan: Complete description: Background, Objectives, Design, Step by Step how the project is going to be done, Data analysis plan:

Means, standard deviations, medians, interquartile ranges (IQR) and ranges will be calculated for interval variables. These variables include patient characteristics and physiological measurements such as age, weight, height, BMI, and pregnancy weight gain. Frequency distributions will be calculated for nominal variables that include race/ethnicity, and parity.

Null hypothesis H01 will be tested by a mixed effects repeated measures analysis of variance (rANOVA) controlling for location and treatment group. In the event the null hypothesis is rejected, contrasts will be used to investigate sub-group differences. The significance level of multiple comparison tests will be corrected to  $\alpha = .05$  by the Holm method. (11) Null hypotheses H02 to H04 will be tested with a two sample t-test or Mann-Whitney U test depending on whether the data is distributed normally or non-normally.

[name], Senior Research Biostatistician Subject Matter Expert for Clinical Research Management under contracts OMNI 0004 3-82 and OMNI 0005 3-126, is the statistical consultant supporting this study. Statistical analysis will be performed with R Version 3.5.1. (12)

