### 9.2 Background and Significance:

Include a literature review that describes in detail the rationale for conducting the study. Include descriptions of any preliminary studies and findings that led to the development of the protocol. The background section should clearly support the choice of study variables and explain the basis for the research questions and/or study hypotheses. This section establishes the relevance of the study and explains the applicability of its findings

Diastasis rectus abdominus (DRA) is a common finding among pregnant and postpartum women (3,6). A small number of studies have shown a correlation between DRA and reduced abdominal wall functioning and poor overall body image (5, 6); some studies have shown DRA to be associated with lumbopelvic pain (3). A study evaluating natural recovery of DRA after pregnancy showed some improvement in DRA and abdominal wall function compared to baseline, but did not return to baseline levels (6). DRA-specific exercise protocols have not been consistently effective in improving associated lumbopelvic pain and it is

unclear if abdominal functionality is improved (1, 2, 6). Ultrasound can be used to noninvasively and accurately measure DRA (3, 4, 5, 7). With general therapy, microcurrent treatments have been shown to improve muscle function and may reduce pain associated with muscular dysfunction, however no studies that we are aware of are using microcurrent to treat DRA. We wish to determine if frequency specific microcurrent treatment is an effective treatment for DRA. Secondarily we will assess lumbar and/or pelvic pain levels, urogynecologic symptoms, and overall body image after having microcurrent therapy. The significance of improving DRA in the postpartum military population may be that the service member can return to exercise sooner without pain and have improved strength, thereby allowing her to return to duty and meet military fitness standards

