**Visit 1 (may be the same day as screening visit):**

- We will apply ultrasound gel and measure inter-rectus distance (IRD), 2 cm above and 2 cm below the umbilical ring, via ultrasound or if unable via ultrasound, via palpation and measuring tape.

-Begin treatment according to randomization group, patients will be instructed to leave microcurrent in place until treatment is over. Subjects will return to the clinic the day after visit 1 so that Research personnel can retrieve the microcurrent box. We will apply ultrasound gel and measure inter-rectus distance (IRD), 2 cm above and 2 cm below the umbilical ring, via ultrasound or palpation with tape measure (measurement will be the same technique as the original measurement).

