**11.0****Statistical/Data Analysis Plan****11.1 Statistical Considerations:**

List the statistical methods to be used to address the primary and secondary objectives, specific aims, and/or research hypotheses. Explain how missing data and outliers will be handled in the analysis. The analysis plan should be consistent with the study objectives. Include any sub-group analyses (e.g., gender or age group). Specify statistical methods and variables for each analysis. Describe how confounding variables will be controlled in the data analysis

The primary outcome measures are inter-rectus distances (IRD) taken 2 cm above and 2 cm below the umbilical ring. Secondary outcome measures taken once at the final postpartum visit between weeks 4 and 12 are Body Image States Scale (BISS); Pelvic Floor Impact Questionnaire- short form 7 (PFIQ-7); and Defense and Veterans Pain Rating Scale for lumbar pain and pelvic pain (DVPRS). Employing these outcome measures, the statistical null hypotheses are as follows:

- H01 — there are no differences in IRD means between times, locations and treatment groups
- H02 — there are no differences in BISS means between treatment groups
- H03 — there are no differences in PFIQ-7 means between treatment groups
- H04 — there are no differences in DVPRS means between treatment groups

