## 11.5 Please provide a justification for your sample size

Subjects will be a random sample of patients meeting the inclusion criteria. Subjects are presumed to be a random representation of the population of patients obtaining similar care at this and other Air Force medical treatment facilities. The main treatment effect is treatment using microcurrent electrical neuromuscular stimulation. Group 1 will receive a placebo effect and Group 2 will receive the treatment effect.

The study is organized as a mixed effects, randomized complete block design with repeated measures. Subject is a random effect as subjects will have been randomly subject to DRA from the population of patients obtaining similar care at these Air Force medical treatment facilities, randomly enrolled from this population of patients, and randomly assigned to treatment groups at the time of enrollment. Fixed effects are treatment group, time of repeated measure, and IRD location as these effects cannot be generalized to other treatments, times or locations.

A priori power was assessed using G\*Power Version 3.1.9.3. (9) The researchers wish to detect at least a 30% difference in IRD between the treatment groups. The mean (SD) IRD at the four locations at 7 weeks postpartum has been estimated to be 1.97 (0.71) cm, 2.39 (0.59) cm, 1.99 (0.65) cm, and 1.30 (0.77) cm respectively, and the minimally detectable changes at a 95% confidence level to be 0.45 cm, 0.47 cm, 0.55 cm and 0.36 cm respectively. (10) These are smaller differences, but near the stated research objective; therefore, these will be used as a conservative effect size to estimate a priori power. The results indicate 98 subjects with 3 repeated measures will have a power of 0.801 at  $\alpha = 0.05$  to detect these minimally detectable differences between the treatment groups.

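### The primary IRD analysis pools time, location and treatment in one null hypothesis, names no treatment test, and leaves the pre-treatment IRD unused as a covariate

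*Combined protocol and SAP*

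**What the plan says.** - **Null hypothesis (11.1).** H01 states that "there are no differences in IRD means between times, locations and treatment groups".
- **Test (11.6).** "Null hypothesis H01 will be tested by a mixed effects repeated measures analysis of variance (rANOVA) controlling for location and treatment group". Treatment, the randomised comparison, is worded as something controlled for.
- **After rejection (11.6).** "In the event the null hypothesis is rejected, contrasts will be used to investigate sub-group differences", with Holm correction. The contrasts are not listed.
- **Model (11.5).** "Fixed effects are treatment group, time of repeated measure, and IRD location"; subject is random. No baseline covariate and no treatment-by-time term is named.
- **Schedule (10.1).** IRD is measured at Visit 1 before treatment, then the next day ("Subjects will return to the clinic the day after visit 1 so that Research personnel can retrieve the microcurrent box"), at Visit 2 and at Visit 3. That makes four occasions, each at two locations.
- **Power (11.5).** "98 subjects with 3 repeated measures will have a power of 0.801" for differences between the treatment groups. The three measures are not identified.

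**The concern.** The trial asks whether microcurrent changes IRD relative to sham. Rejecting H01 does not answer that, because H01 is false as soon as IRD changes over time in both arms or differs between the two sites.

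Both are foreseeable from the protocol. Section 9.2 reports that "A study evaluating natural recovery of DRA after pregnancy showed some improvement in DRA and abdominal wall function compared to baseline", so a time trend without treatment is expected. The location means in 11.5 are "1.97 (0.71) cm, 2.39 (0.59) cm, 1.99 (0.65) cm, and 1.30 (0.77) cm respectively", so a site difference is plausible.

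Two further things are at stake:

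- **The deciding test is open.** A group main effect over all occasions, a mean of the post-treatment occasions, and a change from baseline can all be defended under the present wording. Choosing among them after seeing the data could inflate Type I error. Holm prevents this only if the family is fixed beforehand.
- **The role of the pre-treatment IRD is open.** As a covariate it gains precision. As a level of the time factor it dilutes the group main effect, because its expected group difference is zero by randomisation.

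**Working it through.** **Inputs from 11.5.** N = 98, three measures, alpha 0.05. The minimally detectable changes are 0.45, 0.47, 0.55 and 0.36 cm and the SDs are 0.71, 0.59, 0.65 and 0.77 cm, giving d = 0.634, 0.797, 0.846 and 0.468. The within-subject correlation rho is not stated. I use 0.5 because it reproduces the plan's figure, and show 0.3 to 0.8.

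**Formula.** Noncentral F with lambda = (N/4) × effect² / Var(contrast), variances in SD² units; df 1 and 96, or 1 and 95 with a covariate. Calculations are for one location unless stated.

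**1. The plan's own figure.** Group main effect, three measures, full difference at each, d = 0.36/0.77 = 0.4675:
- Var = (1 + 2 × 0.5)/3 = 0.667
- lambda = 24.5 × 0.2186/0.667 = 8.03
- power = 0.801, as stated.

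The other three effects give 0.967 to 0.999, and four measures give 0.826. So 0.801 appears to be a group main effect for the smallest effect. This fixes the number of measures but not which ones they are.

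**2. Pre-treatment IRD as covariate, three post-treatment occasions.** Var = 0.667 − 0.5² = 0.417, lambda = 12.85, power = 0.944.

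The entry rule (IRD of at least 2.5 cm, section 12.5) may narrow the baseline distribution. Truncating a normal with mean 1.30 and SD 0.77 at 2.5 leaves a baseline variance of v = 0.145 of the original. Then Var(post) = 1 − rho²(1 − v) and Cov(post, post′) = rho − rho²(1 − v). The ANCOVA residual variance is unchanged.

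| rho | Untruncated: unadjusted / ANCOVA | Truncated: unadjusted / ANCOVA |
|---|---|---|
| 0.3 | 0.880 / 0.931 | 0.924 / 0.931 |
| 0.5 | 0.801 / 0.944 | 0.926 / 0.944 |
| 0.7 | 0.726 / 0.984 | 0.960 / 0.984 |
| 0.8 | 0.692 / 0.998 | 0.982 / 0.998 |

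The gain is 5 to 31 points untruncated and 0.7 to 2.4 points truncated. Averaging both locations (inter-location correlation 0.5 assumed, rho 0.5, untruncated) gives 0.900 against 0.984. With zero baseline correlation the covariate costs less than 0.001.

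**3. Pre-treatment IRD as a response level, group main effect, rho 0.5.**
- Visits 1 to 3: effect × 2/3, lambda = 8.03 × 4/9 = 3.57, power 0.46 (truncated 0.81).
- All four occasions: effect × 3/4, Var = (1 + 3 × 0.5)/4 = 0.625, lambda = 4.82, power 0.58 (truncated 0.89).
- Other three effects: 0.72 to 0.98 untruncated, 0.95 or more truncated.

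**4. Rejecting H01 with no treatment effect.**
- *Time.* For a linear fall Δ over three occasions, lambda = N × (Δ²/2)/(SD²(1 − rho)), df 2 and 192, SD 0.77. Power reaches 80% at Δ = 0.29, 0.24 and 0.15 cm for rho 0.3, 0.5 and 0.8. At Δ = 0.36 cm and rho 0.5 it is 0.989.
- *Location.* Paired comparison at one occasion, lambda = N × δ²/(s₁² + s₂² − 2 × r × s₁ × s₂), with inter-location correlation r of 0 to 0.5. Five of the six pairs of quoted means differ by 0.40 to 1.09 cm, and each gives 0.99 or more. The sixth differs by 0.02 cm and gives about 0.06.
- *Simulation.* 3,000 null-treatment trials per scenario, two locations, four occasions, SD 0.70 and rho 0.5 assumed. H01 counts as rejected if any of the time, location or group F tests has p < 0.05. Rejection is 14% with no effects at all, 96% with a 0.2 cm shared trend, and 100% with a 0.40 cm location difference. The group test alone stays near 5%.

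**5. Choosing the contrast afterwards.** Take the smallest p of three treatment contrasts, each at 0.05: mean of four occasions, mean of three post-treatment occasions, and post-treatment mean minus baseline. In 40,000 null trials at rho 0.5, Type I error is 0.10 to 0.11 untruncated and 0.08 to 0.09 truncated. With Holm over those same three, fixed in advance, it is about 0.04 untruncated.

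**The case against.** A repeated-measures ANOVA gives separate F tests for group, time and location. Section 11.5 powers a group difference, and 0.801 reproduces as the group main effect, so the intended test can be inferred. The group test keeps its level, and a time or location effect becomes a false efficacy claim only if it is misreported as one. Omitting a covariate is valid. The 14-point gain applies to the smallest effect without truncation; for the other three effects unadjusted power at rho 0.5 is already at least 0.967, and adjustment adds at most about 3 points. The truncated case is also artificial: only about 6% of a normal with mean 1.30 and SD 0.77 lies above 2.5 cm.

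Much of this stands. The covariate is an efficiency point whose size is uncertain, and the inflation in step 5 is what the wording permits, not what the plan prescribes. But intent inferred from a power paragraph does not declare a primary test. Sections 11.1 and 11.6 still tie the primary conclusion to the pooled null, and Holm has no fixed family to act on. Nor does the text settle which three measures were powered. Section 10.1 calls the pre-treatment value the original measurement, which leans towards three post-treatment occasions, but that phrase concerns measuring technique.

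**Conclusion.** The concern holds and should be fixed. As written, rejecting H01 is not evidence of a treatment effect, and no treatment term is declared primary. This follows from the text and needs no assumed correlation.

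The sizes are conditional on an inferred d and rho, and on how the entry rule acts. On the likelier reading, with three post-treatment occasions, the stated 0.801 stands and the unused baseline costs about 2 to 14 points at rho 0.5 for the smallest effect. If the pre-treatment value is a response level, the stated power does not carry over to an untruncated group main effect at that effect size. The protocol does not name the four quoted locations or say where the 2.5 cm rule applies, and section 9.2 gives no size for natural recovery. The figures are therefore ranges, not predictions. Confidence is medium.

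**What to change.** **In 11.1 and 11.6:**
- Model post-treatment IRD (day after, Visit 2, Visit 3; both locations) with treatment, time, treatment-by-time and location as fixed effects, pre-treatment IRD at the same location as covariate, and subject as random effect.
- Restate H01 as no baseline-adjusted group difference averaged over the post-treatment occasions and both locations, and name this as the single primary treatment test. If the sponsor prefers a named visit to the average, that also works, provided it is declared before unblinding.
- Report time and location effects descriptively, and list any further contrasts as a fixed Holm family.

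**In 11.5:** state the occasions, effect size and correlations used, and restate power for this model. As a sensitivity case, apply the 2.5 cm entry rule consistently to variances and correlations.

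**Cost:** SAP wording and a rerun of the power calculation. No new data, visits or patients.

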**Screening visit (within 3 months postpartum):**

- Obtain and document signed Informed Consent and HIPAA authorization.
- Review past medical and pregnancy history to verify inclusion and exclusion criteria.
- Collect demographic information to include age, weight (pounds), height (inches), BMI, DoD ID#, current email address (for scheduling), phone number, race, ethnicity.

**Randomization:** Subjects will be randomized into one of two research treatment groups with approximately 58 subjects in each arm:

- Group 1: Sham (fake) microcurrent therapy (placing the microcurrent pads on the patient and turning the microcurrent box on placebo mode ), for one treatment lasting a total of 7 hours and 10 minutes the device will worn at home and returned.
- Group 2: Frequency specific microcurrent therapy (100-300 $\mu$ A microcurrent amps) with Diastasis Recti Repair protocol (8), for one treatment lasting a total of 7 hours and 10 minutes the device will be worn at home and returned.

**Blinding:** [name] will be responsible for managing the excel spreadsheet that randomly assigns the patient to Group 1 or Group 2. She will place the randomization code into a sealed envelope and deliver it to the Research Technicians who will program the microcurrent boxes to either Group 1 (Sham microcurrent therapy) or Group 2 (microcurrent therapy). The blinded microcurrent boxes will be provided to the study staff to apply the microcurrent treatment. The remaining study staff will be blinded to the study treatment. If at any time a patient experiences an adverse event that requires breaking of the blind, [name] can provide the randomization assignment. At the conclusion of the study, and once all the subjects have completed treatment and follow up, [name] will provide the randomization assignments to the study staff to be included in the data analysis.

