## 12.5 Inclusion Criteria:

Order Number	Criteria
1	
 
-Active Duty and DoD beneficiary Postpartum Females (within 3 months postpartum) with Diastasis Rectus Abdominus (DRA) pain
 
-IRD greater than or equal to 2.5 cm
 
-Aged 18 years or older
 
-Singleton gestation/delivered (one baby carried and born)
 
-Vaginal delivery
 
-Nulliparous (first pregnancy) or multiparous (more than one pregnancy in the past)
 

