## 12.6 Exclusion Criteria:

Order Number	Criteria
1	
 
-less than 18 years of age
 
-females greater than 3 months post-partum
 
-Medical history to include pacemaker
 
-History of arrhythmia
 
-Transplant status
 
-Insulin pump
 
-Pain pump
 
-Active cancer
 
-IRD less than 2.5 cm
 
-Inability to measure IRD
 
-Delivery via caesarean section
 
-Operative vaginal delivery (vacuum or forceps)
 
-3rd or 4th degree vaginal laceration
 
- Inability to return the microcurrent device
 

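### Entry runs to 3 months postpartum but weeks since delivery is not in the H01 model; prespecifying it is a nearly free, small gain in precision

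*Combined protocol and SAP*

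**What the plan says.** - **Entry.** Section 12.5 admits "Postpartum Females (within 3 months postpartum) with Diastasis Rectus Abdominus (DRA) pain" and section 12.6 excludes "females greater than 3 months post-partum". The screening visit in 10.1 has the same limit. No lower limit or stratification by time since delivery is given.
- **Natural course.** Section 9.2 reports: "A study evaluating natural recovery of DRA after pregnancy showed some improvement in DRA and abdominal wall function compared to baseline". It gives no rate.
- **H01 model.** Section 11.6: "Null hypothesis H01 will be tested by a mixed effects repeated measures analysis of variance (rANOVA) controlling for location and treatment group". Section 11.5 makes subject a random effect and says: "Fixed effects are treatment group, time of repeated measure, and IRD location".
- **H02-H04.** "Null hypotheses H02 to H04 will be tested with a two sample t-test or Mann-Whitney U test", according to distribution (11.6). These outcomes are taken once, at the final visit (11.1).
- **Power.** Section 11.5 starts from values at a single time after delivery: "The mean (SD) IRD at the four locations at 7 weeks postpartum has been estimated to be" 1.97 (0.71), 2.39 (0.59), 1.99 (0.65) and 1.30 (0.77) cm. It states power of 0.801 for 98 subjects with 3 repeated measures.
- **Measurement schedule.** Section 10.1 sets IRD measurements at Visit 1 before treatment, the day after Visit 1, Visit 2 and Visit 3. That is four, and 11.5 does not say which three it means.
- **Data list.** Section 10.2 does not name weeks since delivery. It does list pregnancy history, and the delivery date is needed to apply the entry limit.

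**The concern.** Time of repeated measure is the study visit. Two women at Visit 1 may be 1 week and 12 weeks past delivery and still carry the same value of every fixed effect apart from treatment group. If IRD falls with time since delivery, as 9.2 suggests, part of the variation between women is predictable at entry, yet it stays in the error term of the between-group comparison. The study is planned at 0.801 with almost no margin, so precision that is already paid for is worth using. What is at stake is a little power for the overall group difference in IRD. The within-woman change over visits is not affected, because a stable difference in entry time cancels from it.

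**Working it through.** **1. The plan's figure.** Smallest standardized effect in 11.5: 0.36/0.77 = 0.468, so f = 0.36/(2 × 0.77) = 0.234. With N = 98, m = 3 and correlation ρ = 0.5 (not stated in the plan; assumed):

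λ = f² × N × m / (1 + (m − 1)ρ) = 8.03, and F(1, 96) gives power 0.8012. This matches the stated 0.801.

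**2. Cost of a covariate that explains nothing.** F(1, 95) with the same λ gives 0.8011.

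**3. Which comparison can gain.** In a simulated mixed model where weeks since delivery explained about 13% of the variance of a woman's mean, the covariate cut the standard error of the overall group effect from 0.126 to 0.119. The treatment-by-time standard error was 0.1386 with and without it.

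**4. Variance explained among eligible women.** Assumptions: linear recovery of 0.02 or 0.05 cm per week; ρ = 0.5; uniform entry over 0-13 weeks; Visit 2 uniform over 2-4 weeks and Visit 3 uniform over 4-12 weeks after treatment; only women with Visit 1 IRD of at least 2.5 cm kept. Week-7 mean (SD) is taken from three of the four locations in 11.5. For the mean of Visits 1, 2 and 3:

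| Week-7 mean (SD) | cm/week | SD of mean | R² | Power at 0.24 cm, unadjusted to adjusted |
|---|---|---|---|---|
| 2.39 (0.59) | 0.02 | 0.361 | 1.3% | 0.903 to 0.906 |
| 1.97 (0.71) | 0.02 | 0.409 | 0.8% | 0.821 to 0.824 |
| 1.30 (0.77) | 0.02 | 0.414 | 0.6% | 0.810 to 0.812 |
| 2.39 (0.59) | 0.05 | 0.380 | 7.2% | 0.871 to 0.894 |
| 1.97 (0.71) | 0.05 | 0.422 | 4.5% | 0.796 to 0.814 |
| 1.30 (0.77) | 0.05 | 0.425 | 3.3% | 0.790 to 0.803 |

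Example, fourth row: λ = (98/4) × (0.24/0.380)² = 9.77, power 0.871. Adjusted, λ = 9.77/(1 − 0.072) = 10.53 on F(1, 95), power 0.894.

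**5. Which measurements enter.** The table assumes no effect at Visit 1, which precedes treatment, and leaves out the next-day IRD: 0.36 × 2/3 = 0.24 cm. The schedule in 10.1 allows other readings, taking the effect as present at every post-treatment measurement:

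- All four measurements: 0.36 × 3/4 = 0.27 cm. Power 0.870-0.958 unadjusted, gain 0.2-1.6 points.
- The three post-treatment measurements: 0.36 cm. Power 0.913-0.988 unadjusted, gain 0.1-1.0 points.
- Visits 1, 2 and 3 only: 0.24 cm. Power 0.790-0.903 unadjusted, gain 0.2-2.3 points.

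**6. Sensitivity.** Even at 0.24 cm, entry over 0-6 weeks gives at most about 0.6 points and over 0-4 weeks about 0.3. At ρ = 0.9 with 0-13 week entry, R² for the three-visit mean is 0.2-3.6%; with short entry windows at that correlation the gain is smaller still.

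**7. Comparison with Visit 1 IRD as a covariate.** For the mean of Visits 2 and 3, Visit 1 IRD explains about 7-17% of the variance at ρ = 0.5 and 46-70% at ρ = 0.9. Weeks since delivery then adds at most about 3.6 percentage points, or 0.2 at ρ = 0.9.

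**The case against.** The strongest case against the point is that it hardly matters. The slope, its linearity, uniform entry and the correlation are all assumed. The largest gain depends on leaving out a measurement that 10.1 schedules. If the visit windows count from delivery, as 9.4 and 11.1 can be read, entry would have to fall within about 4 weeks and the gain is at most about 0.3 points. Visit 1 IRD is already collected and is the stronger covariate. All of this stands and limits the size of the point. It does not remove the omission or raise the cost of the remedy.

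Stronger readings are tempting, and the documents do not support them:

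- **Bias.** A reader might infer that uneven entry times confound the comparison. Allocation is randomized, so entry time is balanced in expectation.
- **Power falling to 0.767.** Adding entry-time variance to the plan's SD of 0.77 gives this. The variance of a woman's mean is 0.593 × 2/3 = 0.395, and (0.05 × 3.75)² = 0.035 adds 8.9%; at 0.02 cm per week the result is 0.796. That SD takes no account of the 2.5 cm entry threshold, and eligible women are less variable (step 4).
- **A flaw in H02-H04.** These tests are unadjusted and lack a baseline, but 9.2 describes recovery of diastasis and abdominal wall function, not of BISS, PFIQ-7 or DVPRS scores. Any gain there is unquantified.

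**Conclusion.** The point holds as a low-priority suggestion. Weeks since delivery is a plausible predictor of IRD on the protocol's own account, will be known at entry, and is absent from the H01 model. The consequence is a small loss of precision in the between-group comparison: between about 0.1 and 1.6 points of power on the two readings that use the next-day measurement, and up to 2.3 on the one that leaves it out. These figures rest on the assumed slope, correlation and entry distribution. The documents cannot confirm them, and a steeper recovery would raise the gain. The planned analysis remains valid without the change.

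A separate, minor matter is the time origin of the visits. Sections 9.4 and 11.1 use postpartum wording, while the Visit 2 and Visit 3 windows in 10.1 state no origin. Counted from delivery, a woman treated after week 4 could not have Visit 2 within its window. The sections need to be reconciled.

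**What to change.** - **11.6:** prespecify weeks since delivery at treatment as a baseline covariate in the H01 model, fixed before the blind is broken so that the adjustment cannot look selective.
- **10.2:** name the variable and state that it is derived from the delivery date needed for eligibility.
- **11.5 or 11.6:** say which IRD measurements are the three repeated measures. If Visit 1 IRD is to serve as a baseline covariate instead of an outcome, say so; weeks since delivery then adds little.
- **H02-H04:** keep the planned tests. An adjusted comparison (linear model, or a rank-based version if non-normal) is optional and should be labelled supportive.
- **9.4, 10.1 and 11.1:** state one time origin for the Visit 2 and Visit 3 windows.

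Cost: one degree of freedom (0.8012 to 0.8011), one line in 10.2, and no new visit or procedure. Limit: the covariate captures entry time only. In the same simulated cases, the spread of Visit 3 over its window explains 0.4-4.1% of Visit 3 IRD variance, which this covariate does not absorb.
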